**Patient confidentiality.**

Paper and electronic case report forms and transcripts. Patients' confidentiality will be protected in multiple ways. First, all study subjects will be assigned a code that cannot be tied to personal identifiers and this code will appear on all study-related materials. The personal identifiers tied to these codes will be known only to study personnel and will be stored in a password-protected program. All other deidentified materials will remain in a locked office in a locked cabinet. All electronic documents will be password-protected.

As part of the consent process, the procedures for obtaining outcome data as well as the safeguards for maintaining confidentiality and minimizing invasion of privacy will be fully described to potential participants. Participants will not have to answer any question they do not want to answer. Participants will be given the contact information for the research staff to answer any questions they might have about the study and consent process. To further minimize risk, the PI will train the RA on potential breach of confidentiality specific to this study and study environment and will assure that all study personnel complete and maintain Human Subjects Protection certificates. The PI will periodically monitor adherence of these principles during a random sample of visits.

Audio files. Digital audio files (focus groups, audio recorded office visits and interviews) will be downloaded as a media file and stored on the PIs password-protected personal computer. Digital audio files will be assigned a code tied to personal identifiers. The personal identifiers tied to these codes will be known only to study personnel and will be stored in a separate password-protected program. We will transcribe all focus groups and individual interviews and some/all office visits. The transcriptionist is an approved Columbia vendor and has provided services in support of Phase I of this trial. The same standards will apply this this second phase: Audio files of the interviews and office visits will be deposited to the Columbia-approved transcription vendor's

dropbox. The vendor has a confidentiality agreement that all employees sign stating that they may not share anything about any of the work that they transcribe with anyone. The vendor will then deposit the transcript in a word document in the drop box for the PIs retrieval. When it has been ascertained that the transcript is a verbatim representation of the interview/office visit the PI will notify the vendor to destroy all files. A copy of the transcript will be maintained by the PI as described in the protocol.

Equipment. After downloading digital audio files, the digital recorder's memory will be cleared. The memory of the spirometer will be cleared of lung function results after a copy has been printed and entered into the electronic data base. Subjects who have the Doser™ electronic ICS monitor will have the dose counter cleared monthly after a record of its use has been transcribed to spread sheets that will be stored in a password-protected program.

Data management, data entry and integrity. An electronic study database (REDCap) will be created and maintained on the password-protected research server at Columbia University. Data entry personnel will receive standardized training on data entry. The Project Manager and RA will be trained and monitored by the PI with periodic checks for drift in standardized practices. If drift is observed they will be re-trained. The study's statistician ([name]) will receive deidentified data transferred via secured communication.

Data entry into desktop computers will be equipped with password lockout and screen savers which activate if the computer is on but not in use for 15 minutes. All study personnel will have their own unique usernames and passwords. All servers are located in a secure datacenter, with necessary redundancies. The server is behind a firewall and is registered as a "Critical Host" by the University. This means Columbia follows all University policies regarding critical hosts: firewalls, access controls, timely patch management and anti viral scans and software updates, and an enterprise system monitoring solution (allowing us to detect and address intrusion attempts). All servers have HIPAA compliant

security. School of Nursing computers operate under a managed desktop solution which is locked down, including hard drive and thumb drive encryption. The base image includes, but is not limited to, Windows 7 with current patches and Antivirus software (which is updated every 4 hours).

Publication or presentation of study findings. Aggregate group data will be used, free of identifiable features, in any publication or presentations that arise from this research.

**c. Procedures for identifying, reviewing, and reporting adverse events and unanticipated problems to the IRB and NINR, the type and number of events that would halt accrual and would generate a review of eligibility, monitoring, assessments, intervention, and how the resumption of accrual would occur.**

All study personnel will report any study-related adverse reactions and/or unanticipated problems involving risks to the PIs as soon as they occur. The PI and/or study researchers will review all data collection forms on an ongoing basis for data completeness and accuracy as well as protocol compliance.

During the trial, subjects will be instructed to notify the study team within 48 hours of any Emergency Department (ED) visit or hospitalization, regardless of its cause, and to notify the study team within 48 hours of initiating oral corticosteroids (OCS), each event representing the standard definition of asthma exacerbation. Because not all exacerbations cause individuals to seek acute care, we will track OCS use as those who manage an exacerbation outside of the ED or hospital will manage their exacerbation with OCS. In this manner we will not miss any exacerbations. To that end, we will also ask subjects to report these at monthly data collection points in an attempt to capture any exacerbations that might otherwise go unreported. Subjects' answers will then be compared to the medical record and/or claims data, as available.

Because there are 1.75 million ED visits annually (7%) among 24 million individuals with asthma we could anticipate a rate of 1.7% ED visits in a 3 month trial. However, only individuals with uncontrolled asthma will be eligible for enrollment so we will plan for 5% of our subjects to have an ED visit for asthma at some time during the 3 month trial. Therefore, data on adverse events, including serious adverse events (SAEs) that meet the standard definition of asthma exacerbation (ED visits, hospitalizations, and OCS initiation), will be reviewed. Exacerbation rates as meeting any of the three standard definitions of asthma exacerbation (ED visits, hospitalizations, and OCS initiation) in excess of the threshold set by the SMC will trigger an immediate study shutdown (see below). AEs and SAEs will be systematically assessed at all data collection points via review of the medical record and/or patient interview. Subjects will be instructed to report AEs and SAEs to the study team within 48 hours of their occurrence. This information will then be shared with the SMC in real-time, as well as additional information about the event that the study team can obtain from the PCP or from the medical record, as available. The SMC will then determine how an AE is to be categorized using standard taxonomy: Unrelated (clearly not related to the research), Unlikely (doubtfully related to the research), Possible (may be related to the research), Probable (likely related to the research) and Definite (clearly related to the research).

The SMC will use the following definitions:

Adverse events are defined as unanticipated problems involving risks to study participants or others, or as any untoward medical occurrence that may present itself during the study time period which may or may not have a causal relationship with the treatment.

Serious adverse events result in any of the following outcomes: death, a life threatening experience, inpatient hospitalization, or a significant disability/incapacity. Such events also include breeches of confidentiality.

Moderate adverse events are those discomforts severe enough to cause interference with usual activities or requiring treatment by a health care provider. Such events also include the loss of participants from the study for reasons related in any way to a deviation from procedures for ensuring confidentiality.

Mild adverse events are those events that are easily tolerated signs or symptoms of discomfort; minor irritants that cause no loss of time from normal activities; symptoms that require no medication or a medical evaluation; and transient signs and symptoms.

Unexpected adverse events are those events, the specificity or severity of which is not consistent with the risk information described in the general investigative plan or the IRB proposal. "Unexpected" refers to an adverse event that has not been previously observed.

Expected adverse events are those events, the specificity or severity of which is consistent with the risk information described in the general investigative plan or IRB proposal.

Any ED visit or hospitalization associated with primary ICD-10-CM Diagnosis Code 493. Asthma (493.00 asthma atopic unspecified; 493.01 asthma atopic asthmaticus; 493.02 asthma atopic acute exacerbation; 493.10 intrinsic asthma unspecified; 493.11 intrinsic asthma asthmaticus; 493.12 intrinsic asthma acute exacerbation; 493.20 asthma chronic

obstructive pulmonary disease copd; 493.21 asthma chronic obstructive pulmonary disease copd; 493.22 asthma chronic obstructive pulmonary disease copd; 493.81 exercise induced bronchospasm; 493.82 cough variant asthma; 493.91 asthma bronchial allergic nos asthmaticus; 493.92 asthma bronchial allergic nos acute exacerbation) will be characterized as a Probable or Definite SAE.

#### SAE reporting.

Any SAE, whether or not related to study intervention, will be reported to the IRB and the SMC. The PI will inform the IRB and SMC immediately and jointly make a decision whether the reported event is a SAE that must be reported to NINR due to the unexpectedness and/or the severity of the event. The initial SAE report will be followed by submission of a completed SAE report to NINR within two days (refer to Table 1. Adverse Events Form, Table 2. Adverse Events Coding, and Table 3. Matrix for Adverse Events Reporting).

In the event that a patient either withdraws from the study or the investigator decides to discontinue a patient due to SAE, the patient will be monitored by the investigator via ongoing status assessment until 1) a resolution is reached, i.e., the problem requiring hospitalization has resolved or stabilized with no further changes expected; 2) the SAE is determined to be clearly unrelated to the study intervention; or 3) the SAE results in death. Outcome of SAEs will be periodically reported to the IRB and to the funding agency. A summary of the SAEs that occurred during the previous year will be included in the annual progress report to the IRB and the SMC. The report will include the participants' sociodemographic characteristics, expected versus actual recruitment rates, treatment retention rates, any quality assurance or regulatory issues that occurred during the past year, summary of AEs and SAEs, and any actions or changes with respect to the protocol.

Table 1. Adverse Events Form

Participant number	AE	Onset Date	Ending Date	*Severity	*Relatedness to Study	*Action	*Outcome	Comments

Table 2. Adverse Events Coding

Severity	Relatedness	Action Taken	Outcome
1=mild	0=Definitely unrelated	0 = None	1=Resolved
2=moderate	1=Unlikely	1 = Referral to Health Center for evaluation	2=Recovered
3=severe	2=Possibly related	2 = Referral to Emergency Evaluation	3=Condition still present and under treatment
4=life threatening	3=Probably related		4=Condition continues to worsen
	4=Definitely related		5= Participant died

Stop rules. If the PI, IRB and/or SMC determines that serious adverse events meeting the standard definition of an asthma exacerbation (ED visit; Hospitalization and/or OCS initiation) have occurred in excess of the 5% threshold set for the study, then data collection and study enrollment will be stopped. The SMC and the IRB will be asked to review the study and suggest modifications of the protocol, the threshold limit or other changes. If the SMC

and the Chairperson of the IRB believe that these modifications are adequate for resumption of the study, then the study will resume. NINR will receive a written report within three days of any such suspension and/or resumption of data collection.

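### The 5% stop threshold equals the planned rate of asthma ED visits alone, yet it covers a wider set of events and has no stated unit or denominator

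*Combined protocol and SAP*

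**What the plan says.** All of this is in the DSMP.

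- **Planned rate (section c).** National figures lead to the statement that "we could anticipate a rate of 1.7% ED visits in a 3 month trial". Because only patients with uncontrolled asthma can enroll, the plan then sets this aside: "we will plan for 5% of our subjects to have an ED visit for asthma at some time during the 3 month trial".
- **Shutdown sentence (section c).** The trigger for immediate shutdown is "Exacerbation rates as meeting any of the three standard definitions of asthma exacerbation (ED visits, hospitalizations, and OCS initiation) in excess of the threshold". This sentence leaves the threshold to the SMC and gives no number.
- **Stop rules.** The counted events are "serious adverse events meeting the standard definition of an asthma exacerbation (ED visit; Hospitalization and/or OCS initiation"). If the PI, IRB and/or SMC determines that these "have occurred in excess of the 5% threshold set for the study, then data collection and study enrollment will be stopped". The SMC and IRB then review the study, may suggest changing the threshold, and may allow it to resume.
- **SAE definitions (section c).** "Serious adverse events result in any of the following outcomes: death, a life threatening experience, inpatient hospitalization, or a significant disability/incapacity"; breaches of confidentiality are added. The moderate class includes events "requiring treatment by a health care provider". A separate rule makes any ED visit or hospitalization with a primary asthma code a probable or definite SAE. Neither the SAE list nor the code rule names OCS starts. Yet an earlier sentence in the same section says that "serious adverse events (SAEs) that meet the standard definition of asthma exacerbation (ED visits, hospitalizations, and OCS initiation), will be reviewed".
- **Who sets the threshold.** Section a appoints the SMC to establish it with the PI's input, while Stop rules already states 5%.
- **OCS tracking (section c).** OCS starts are tracked because exacerbations handled outside the ED or hospital are expected to be handled with OCS, and the aim is to miss none.

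**The concern.** A stopping limit is normally placed above the rate the trial expects, so that crossing it signals something unplanned. Here the limit equals the expected rate of one component, while the rule counts three. The plan itself expects exacerbations that never reach an ED or hospital, so a count that includes OCS starts should run above the ED rate. How far above cannot be judged, because no combined rate is given.

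The counted set is also not settled. The stop rule lists OCS starts but applies to SAEs, and the definitions of an SAE do not name them. Two monitors could classify the same OCS start differently. Nor does the rule say whether 5% means subjects or events, or whether it is a share of all 80, of those enrolled to date, or of one arm.

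At stake is a halt to both enrollment and data collection, including the monthly visits that supply the primary outcome, without any rise in ED visits above plan. If OCS starts were left out because of the SAE qualifier, exacerbations that the plan tracks deliberately would fall outside the rule.

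**Working it through.** **Inputs.** 1.75 million ED visits a year among 24 million people with asthma, given as 7% (DSMP section c); planned rate 5% over 3 months (same section); threshold above 5% (Stop rules); 80 patients, two groups of 40 (Power & Sample Size); 10% attrition (same section).

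**The plan's own figure.** 7% / 4 = 1.75%, which the plan gives as 1.7%. It reproduces up to rounding. The step from there to 5% is a planning judgment and is not derived. The calculations below use 5%, the rate the plan adopts for this population.

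**What the limit means with 80 subjects.** 0.05 × 80 = 4.0, so exceeding 5% means 5 or more subjects with an event. The expected number at the planned rate is also 80 × 0.05 = 4.0.

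**One check on all 80 (assumed).** With X ~ Binomial(80, 0.05):

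- P(X = 0), ..., P(X = 4) = 0.0165, 0.0695, 0.1446, 0.1978, 0.2004
- P(X ≥ 5) = 1 − P(X ≤ 4) = 0.371

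So a count made up only of ED visits, at exactly the planned rate, passes the limit 37% of the time.

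**Running denominator, checked after each subject (assumed).** Subjects are counted one at a time and the halt occurs the first time events / n exceeds 0.05, for n = 1 to 80. An exact recursion at a true rate of 5% gives 0.800, or 0.717 if checks begin at n = 20. Much of this comes from early counts: 1/19 = 5.3%, so one event among the first 19 subjects is enough, and 1 − 0.95^19 = 0.62.

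**Other denominators, also at a true rate of 5%.** The plan names neither of these; they show only how much the answer depends on the choice.

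| Denominator | 5% of n | Halt at | P(halt) |
|---|---|---|---|
| 80 | 4.0 | 5 or more | 0.371 |
| 72 (after 10% attrition) | 3.6 | 4 or more | 0.488 |
| 40 (one arm) | 2.0 | 3 or more | 0.323 |

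**Adding other events.** Subjects who are hospitalized or start OCS without an ED visit raise the counted rate above 5%. The documents give no figure, so these rates are assumptions: with 80 subjects and one check, P(X ≥ 5) is 0.725 at 7.5% and 0.912 at 10%.

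All figures treat subjects as independent and ignore clustering by PCP.

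**Does an OCS start count?**

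| Text in the DSMP | OCS start |
|---|---|
| Shutdown sentence, section c | Named |
| Stop rules, list of events | Named, under an SAE qualifier |
| Sentence on SAEs to be reviewed, section c | Named |
| SAE outcome list, section c | Not named |
| Asthma diagnosis-code rule, section c | Not named (ED visits and hospitalizations only) |
| Moderate class, section c | Not named, but the wording can cover it |

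**The case against.** The strongest reply is that this is a cautious trigger in a small feasibility pilot, that it needs a determination by the PI, IRB or SMC, and that it leads to a review with power to change the threshold and resume. The SMC is also charged with setting the threshold. All of that stands and softens the harm. It does not remove the mismatch: Stop rules already fixes 5%, and once an excess is determined the halt is not optional.

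A reader might infer that the shutdown sentence in section c and Stop rules contradict each other on OCS starts. They do not, since both list them. The tension is between that usage and the SAE definitions. The reading that counts OCS starts is the more natural one, because the rule names them; the exclusion reading is weaker but is left open by the SAE qualifier.

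A reader might also think that asthma ED visits without admission are in doubt, because the SAE outcome list omits them. The diagnosis-code rule settles that asthma-coded ED visits are SAEs.

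It is fair to say that 37% depends on a single check. Section c has events sent to the SMC in real time and an immediate shutdown, which fits repeated looks at least as well. That points to a higher chance, not a lower one.

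**Conclusion.** The point holds. The stop threshold equals the planned rate of asthma ED visits but is applied to ED visits, hospitalizations and/or OCS starts, with no combined expected rate, no stated unit or denominator, and an SAE qualifier that does not match the SAE definitions. With the counted rate at the planned 5% and nothing added, the chance of a halt is 37% (80 subjects, one check) and about 80% with a running proportion checked after every subject. Both schedules are assumptions, and independence between subjects is assumed. Additional subjects with only an OCS start or a hospitalization raise these figures.

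Two stronger readings are not supported. The national 1.7% should not be used as a low-end scenario for this trial, because the plan sets it aside for a population with uncontrolled asthma. And it cannot be said that an SMC review schedule or a denominator is absent from the whole plan, because part of the DSMP near the SMC membership list is not in the text reviewed.

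This should be fixed before enrollment. It is a flaw in a decision threshold, tempered by the provisions for review and resumption.

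**What to change.** Before enrollment, reconcile DSMP section a, section c (OCS tracking, planned rate, shutdown sentence, SAE definitions and diagnosis-code rule) and Stop rules, so that:

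1. the expected rate and the stop threshold refer to the same event set;
2. the unit (subjects or events) and the denominator are stated for both;
3. the text says whether an OCS start counts despite the SAE qualifier;
4. it is clear whether 5% is the SMC's threshold or a provisional figure.

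The SMC should then confirm the threshold after seeing the chance of a halt at the expected rate for that event set, under the way checks will actually be made. No replacement threshold is proposed here.

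The cost is DSMP wording and one SMC confirmation, with no added procedures or visits.

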**Step 4: Shared decision-making (2 minutes).** The PCP and patient jointly consider treatment options. The PCP will actively attempt to build consensus around ICS adherence, reconciling conflicts to better align beliefs with evidence-based guideline-directed ICS treatment. For example, if the patient uses ICS intermittently (rather than the required twice-daily dosing) because of an erroneous belief that tolerance to ICS develops with daily dosing, then the PCP will attempt to counter that belief using responses gleaned from the CBPR development phase (focus groups) and information from national guidelines. This will likely include encouraging the patient to use ICS once a day (50% adherence) as an initial short-term plan to be followed by a return visit and re-evaluation of asthma control. If the patient declines to engage in shared decision-making or declines attempts at negotiating ICS use, then the PCP and the patient agree to disagree. This is a one-time intervention.

**Usual care with an attention control condition.** Patient codes associated with PCPs randomized to the attention control condition will trigger the tablet to load a 7-minute timer for the PCP to use to track the length of the attention control condition (discussion of healthy lifestyles). Control PCPs will have access to all the data that the active intervention PCPs have: the ACQ score, CAM-A results, and lung function results. To control for contact, they will be instructed to engage in a 7-minute diet and exercise discussion as this will not confound results and it was a common topic in our prior study; ICS adherence was not discussed.

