## **DSMP**

The proposed study includes (1) a development phase where we will develop the intervention using focus groups with patients and patients' family/support persons (N = 60) with primary care provider (PCP) review, and (2) a pilot validation phase where we will conduct a pilot randomized controlled trial with 8 PCPs from Philadelphia primary care clinics randomized to one of two study arms: (1) the **BREATHE** intervention, or (2) usual care. We will follow 10 Black adult patients with uncontrolled asthma per PCP (N = 80) for three months post-intervention. Post-study refinement will include additional interviews with patients, family/support persons and PCPs who did and did not participate.

This Human Subjects Research meets the NIH definition of "Clinical Research." Institutional review board (IRB) permission for the study will be obtained from the Columbia University (IRB of record) and will be reviewed annually. Although the NIH requires data and safety monitoring for any clinical trials, having an Safety Monitoring Committee (SMC) – a small group of 3 experts who are independent of the protocol who review data from a particular study including independent investigators and biostatisticians - may be appropriate if the study includes multiple sites and a vulnerable population. Because the application includes a feasibility trial in urban minority adults from different clinical sites, and because inclusion criteria require that participants have uncontrolled asthma, we will establish an SMC.

**a. Monitoring entity or who will monitor the study.** While the behavioral intervention itself is a low risk intervention, participants must have uncontrolled asthma to be eligible for enrollment. Because of this, we will appoint an SMC to establish a threshold for asthma exacerbations (defined below) with the PI's input. The SMC will be appropriate experts who are independent of the study and available in real time to review and recommend appropriate action regarding adverse events and other safety issues.

The SMC, appointed by the PI and approved by the Program Officer include:

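### The stop rule suspends data collection as well as enrolment, for an unstated time, with no exception for scheduled outcome and safety follow-up of patients already treated

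*Combined protocol and SAP*

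**What the plan says.** **The rule.** Under Stop rules (DSMP, part c), if serious adverse events meeting the exacerbation definition "have occurred in excess of the 5% threshold set for the study", "then data collection and study enrollment will be stopped". Earlier in part c, the same action is described for exacerbation rates "in excess of the threshold set by the SMC will trigger an immediate study shutdown (see below". The SMC and IRB then review the study. If the SMC and the IRB chair "believe that these modifications are adequate for resumption of the study, then the study will resume". No maximum length is given, and enrolled patients are not treated separately.

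**What happens at the visits.** On exacerbations, part c says "we will also ask subjects to report these at monthly data collection points in an attempt to capture any exacerbations". On adverse events generally: "AEs and SAEs will be systematically assessed at all data collection points via review of the medical record and/or patient interview". Patients are also told to report emergency visits, hospital admissions and oral corticosteroid starts within 48 hours.

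**Exposure and follow-up.** Step 4 of the intervention description says "This is a one-time intervention". The opening of the DSMP commits to following patients "for three months post-intervention".

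**Continued monitoring.** The SAE reporting section follows patients to resolution, but only those who withdraw or are discontinued because of an SAE.

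**The concern.** A safety halt should stop new exposure while preserving observation of people already exposed. Here enrolment and data collection stop together. For a patient past Visit 1 there is no study exposure left to stop: in the schedule of assessments, Visits 2 to 4 consist of questionnaires, spirometry, diary and dose-counter collection.

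Two things are at stake. The SMC and IRB would be deciding on modifications and resumption while the scheduled exacerbation questions and adverse-event assessments of treated patients were suspended. And ACQ, FEV1, AQLQ and MARS-A values falling due during the pause would be missed or late, in a pilot meant to estimate parameters for a larger trial.

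**Working it through.** **1. The passages side by side.**

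| Item | Where | Status during a halt, as written |
|---|---|---|
| Enrolment, new Visit 1 sessions | Stop rules | Stopped |
| Visits 2 to 4 outcomes | Stop rules; Statistical Procedures | Stopped, as data collection |
| Monthly exacerbation questions | DSMP part c | Stopped, being placed at data collection points |
| Systematic AE/SAE assessment by record review or interview | DSMP part c | Stopped, for the same reason |
| 48-hour self-report, and enquiry to the PCP or record about a reported event | DSMP part c | Not mentioned; self-report is stated for the duration of the trial |
| Monitoring to resolution | SAE reporting | Only patients who withdraw or are discontinued due to an SAE |
| Intervention exposure of patients past Visit 1 | Step 4 | None remaining |

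**2. The plan's own figures.** The DSMP derives its background emergency-visit rate from 7% a year: 7% / 4 = 1.75%, given as 1.7% (unrounded, 1.75 / 24 / 4 = 1.82%). It then plans for 5%. With 80 patients, 5% is 0.05 × 80 = 4, so the fifth affected patient exceeds the threshold. This counts patients against all 80; the plan does not say whether patients or events are counted, or against what denominator at an interim look. Those choices affect when a halt occurs, not what it does.

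**3. Patients in follow-up at the halt.** Inputs from the documents: 80 patients and follow-up at 1, 2 and 3 months (Statistical Procedures; the Visit 4 column of the schedule shows about 4 weeks after V1, so I used the months). Assumed: accrual of 9, 12 or 18 months, and events uniform over each patient's 3 months. At steady state the number in follow-up is 80 × 3 / accrual months:

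- 9 months: 240 / 9 = 26.7
- 12 months: 240 / 12 = 20.0
- 18 months: 240 / 18 = 13.3

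Simulation (20,000 runs, random uniform entry, halt at the fifth affected patient) gives means of 24, 19 and 13 at a 5% event rate, and 27, 20 and 14 at an assumed 10% rate. Evenly spaced entry gives nearly the same (18 and 20 for 12 months).

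**4. Visits missed.** Visits are a month apart, so each patient in follow-up has exactly one visit due in the next month. For 12-month accrual and 20 patients:

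- One-month pause: 20 × 1 = 20 visits, of which about 20 / 3 ≈ 7 are final 3-month visits.
- Two-month pause: two-thirds miss two visits and one-third miss one, so 20 × (2/3 × 2 + 1/3 × 1) ≈ 33 visits, of which 20 × 2/3 ≈ 13 are final. Simulation gives 31 to 34 visits.
- No resumption: an average of (3 + 2 + 1) / 3 = 2 visits outstanding per patient, about 40 in all. Simulation gives 35 to 40.

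This treats a visit falling in the pause as missed, because the plan states no visit windows or make-up rule. A late visit would not recover everything: the dose counter records 30 days of use and each diary covers 30 days.

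**The case against.** Several stronger readings are tempting, and the documents do not support them.

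- **That a trigger ends the 3-month follow-up.** The rule provides for review and resumption. Follow-up ends early only if the study does not resume or the pause outlasts a patient's window.
- **That all exacerbation capture is switched off.** The monthly questions back up the 48-hour self-report, and the PI remains responsible for participant safety daily. Neither is named as stopped. What stands is that the plan does not say self-report continues through a shutdown, and the monthly questions were added because self-report may miss events.
- **That patients caught by the halt lose their primary outcome.** With 12-month accrual only about 27% to 32% of them have not yet reached Visit 2, so most would already have had at least one follow-up ACQ due.
- **That the missing data bias the comparison.** The rule does not separate the arms, so the halt falls on one calendar date for both. In simulation only about 2 of the 19 to 20 patients caught have had an event; the rest are cut off by date. The mixed models use partial records, and a pause does not contradict the intention-to-treat commitment.
- **That the chance of a halt measures this defect.** With a fixed denominator of 80 and independent patients, the binomial chance of five or more affected is 37% at the 5% planning rate. That figure concerns where the threshold sits, a separate matter, and is not used here.

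It can also be said that stopping everything is cautious, that feasibility is the primary goal, and that the SMC and IRB may already modify the protocol. The last two are true and limit the severity. The first does not hold for patients past Visit 1, from whom the pause removes observation and no exposure.

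**Conclusion.** The point holds as a defect in how the halt operates. As written, the rule suspends scheduled outcome and safety data collection for treated patients, for an unstated time, while the SMC and IRB are deciding what to do. Under assumed 12-month accrual it catches about 19 to 20 patients (13 to 14 for 18 months, 24 to 27 for 9), and a one-month pause misses about one scheduled visit for each. These counts assume a trigger at the fifth affected patient of 80, uniform accrual and uniform event times; accrual and pause lengths are not in the documents. The cost is mainly in precision and safety information, with no demonstrated bias between arms. The wording conflict itself rests on no assumption. It should be corrected, but it does not invalidate the trial.

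**What to change.** Reconcile the Stop rules, the shutdown sentence and exacerbation-capture text earlier in DSMP part c, and the SAE reporting section, so that they state which data continue during a halt. Suggested wording: *When the threshold is exceeded, enrolment and new Visit 1 sessions pause pending SMC and IRB review. Already scheduled outcome and safety data collection for enrolled patients, including the monthly exacerbation questions and 48-hour reporting, continues unless the SMC or IRB directs otherwise.*

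The threshold and all clinical management stay with the SMC and IRB. The cost is a short edit to the DSMP, with no added visits, staff or patients. The small downside is that research assistant visits continue during a pause.
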